## **Funding**

Funding has been secured from a Faculty of Health grant from Victoria University Wellington Ref 22337 which will fund the research nurse and support data collection.

The Universal Trial Number (UTN) is U1111-1249-0775

### Introduction

Project Summary

latrogenic skin injury in hospitalised babies is common. Most babies who are admitted to a Neonatal Intensive Care Unit require a peripheral intravenous catheter (PIVC) for fluids, medication and nutrition. PIVCs (drips) are placed inside a vein and are the most commonly

used device in unwell babies, with many babies requiring multiple drips. PIVCs are secured to the baby's limb using splints and adhesive dressings. Removing the adhesive dressing (Elastoplast) frequently tears the fragile neonatal skin, causing pain, increasing the risk of infection and possibly lasting skin damage. Following a traumatic event experienced by a baby, whānau and staff within the Neonatal Intensive Care Unit at Waikato Hospital. We sought to design a new splint. The Pēpi Splint is made from medical silicone. It secures the PIVC to the baby without the need for adhesive dressings to be applied to the baby's skin.

We propose a stepwise investigation. The first phase is a prospective intervention proof-of-concept pilot study to determine the effectiveness and acceptability of the Pēpi Split. We will recruit 30 Neonatal babies > 1000g who will require a PIVC as part of routine treatment in the Wellington Regional Hospital Neonatal Intensive Care Unit. Babies enrolled in the study will be cared for in the same way as those not in the study, with the addition of the Pēpi Splint. The study will run for as long as the Pēpi Splint remains in place. We estimate this period will vary between babies from 12 to 72 hours. Data will be collected from clinicians about the effectiveness and from the parents about the acceptability of the Pēpi Splint. These data will later be analysed by the Steering Committee. If the Pēpi Splint is found to be effective and acceptable parents, we may proceed to a randomised controlled trial.

It is possible that the we will be able to considerably reduce the incidence of iatrogenic skin injuries in one of our most vulnerable populations, medically fragile babies.

### **Background and rationale**

Skin injuries are the most common iatrogenic injuries in hospitalised babies which increases the risk of infection (local and systemic), and can lead to fluid and electrolyte imbalance and temperature instability. The skin injury can cause complications which prolong hospitalisation and can result in permanent scarring . Peripheral intravenous catheters (PIVCs) are the most common device used in hospitalised, unwell and fragile babies, as intravenous therapy is fundamental to their care. Many babies require admission to hospital. There are approximately 60,000 births annually within New Zealand. Of these babies, 4,500 (8%) are born prematurely and 3,500 (6%) are born smaller than expected. Most of these babies will be admitted to a Neonatal Intensive Care Unit and will require a PIVC for the administration of fluids, nutrition and medications.

PIVCs can be difficult to place and many babies require more than one during their hospitalisation . However, data regarding the duration of PIVCs or the number required for any given baby are few and none within New Zealand. The duration of PIVCs varies from < 12 to 72 hours. Predicting which babies will suffer skin injury has been found to be complex and multifactorial. Reducing harm to those requiring health care is a global health priority.

A key priority of the New Zealand Health Quality and Safety Commission is to reduce the incidence of skin damage in hospitalised patients. Primarily, the focus of this work is in adult patients. Skin injuries in babies are more difficult to assess due the fragility and depth of the skin. Australian authors have recently proposed a skin injury assessment tool. Generally skin injuries related to the use of a PIVC and splint are caused by removing plasters attached to the skin, causing epidermal stripping. Pressure areas can also be caused from the Elastoplast tapes. Extravasation injury occurs when the PIVC migrates from the vein into the tissues, this is a common injury related to the fragility of neonatal veins and the solutions infused via the PIVC, and while it can be, is not generally related to the splint and securing. It is essential that the PIVC insertion site is visible to the bedside nurse

in order to assess for any redness or swelling, as a key priority for the bedside nurse is to reduce the risk of iatrogenic injury.

Should the Pēpi Splint be found to be effective and acceptable we may proceed to either an equivalence or superiority randomised controlled trial comparing the Pēpi Splint with the currently used splint and identify important barriers to changing practice.

### Research outcome

To determine if the Pēpi Splint is effective and acceptable in the clinical environment so that a randomised controlled clinical trial may be performed

Specific aims for Proof of Concept phase

To determine if the Pēpi Splint is effective and acceptable to parents: supports the intravenous catheter and does not cause any skin redness or damage Is acceptable to parents

### Trial design

Proof of Concept, prospective intervention study

### **PICOT**

Participants	Neonates ≥30 weeks' gestational age, > 1000 g and admitted to the Neonatal Intensive Care Unit whom require an intravenous catheter.
Intervention	Application of the Pēpi Splint.
Control	Not required.
Primary outcome	The Pēpi Splint is effective and does not cause harm as
	measured by the bedside clinician
Planned sample size	30 babies
Timing of assessment	Assessment for the primary outcome will be for the duration that
	the Pēpi Splint remains on the baby.

Methods: Participants, Interventions

Study setting Neonatal Intensive Care Unit at Wellington Regional Hospital

### **Inclusion criteria**

Babies requiring the placement of a PIVC

#### **Exclusion criteria**

- Current Weight ≤ 1000 grams
- Gestational age < 30 completed weeks' gestation
- Any skin condition preventing the attachment of the Pepi Splint
- Maior congenital abnormalities
- Terminal conditions

### **Interventions**

### Education

## Clinical staff will be provided with education about the application of the Pēpi Splint

After written informed consent is obtained and an eligible baby requires an intravenous infusion, a clinician will select and apply the appropriately sized Pēpi Splint. There will be two sizes available, for babies weighing  $\leq 2,500$  or > 2,500g. When an enrolled baby requires a PIVC the clinical staff will select the appropriate Pēpi Splint for the size of the baby and apply to the baby. The duration of the study will be from the time that Pēpi Splint is applied until removal of the splint and the exit photos are taken.

### Study Assessments

Bedside nurses currently assess the skin and limbs of babies and in particular the areas of skin where such as PIVCs are in place. In order to minimise increased workload these routine clinical observations and recordings will be used to assess the skin for the duration of the study period 

Detailed data about the Splint will also be collected

A data collection sheet will be completed by a clinician which includes:

- Participant demographic date
- Length of time that the splint was in place
- Whether the Pēpi Splint supported the peripheral intravenous catheter
- Ease of application and removal
- Any concerns regarding the splint
- Perceived comfort level for each participant by both staff and parents
- There will be space for comments
- Photos will be taken with the Pēpi Splint in situ

### Parental questionnaire

Parents will be asked to complete a simple questionnaire about what they liked and disliked about the Pēpi Splint.

Questionnaires will be later electronically entered into a database.

## **Images**

Standardised photos will be taken on a camera of the Pēpi Splint following application and after removal of the splint. All images will include a white tape measure which will allow for colour correction and measurement of any injury. All images will be deidentified and identified only by the participants study number and stored electronically by [name] .

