### Sample size

The primary reason for this Proof of Concept phase is to determine if the Pēpi Splint will support the PIVC and any adverse events related to the use of Pēpi Splint.

We do not expect any adverse events. We have determined that using a sample size of 30 where no adverse events have been observed, we can be assured that the 95% upper band on the rate of adverse events will be less than 10% (3/30 = 0.1). This will provide enough evidence to justify the progression to a randomised controlled trial.

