#### Recruitment

Recruitment will be face to face and babies will be enrolled following admission to the Neonatal Intensive Care Unit. It is likely that most babies will have previously had an PIVC for treatment or fluids. The study will be advertised on posters within the Neonatal Intensive Care Unit and parent information sheets will be available. Research staff and clinicians from the Neonatal Intensive Care Unit will be able to recruit a whānau into the study, most commonly this will be the bedside nurse.

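### The protocol specifies no study record of the limb's skin before the splint goes on, so attributing skin damage to the splint has no defined baseline

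*Protocol*

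**What the plan says.** On what is recorded and when, the protocol states:

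- **Images:** "Standardised photos will be taken on a camera of the Pēpi Splint following application and after removal of the splint". The images carry a tape measure so that an injury can be colour-corrected and measured.
- **Study Assessments:** the data collection sheet lists photos with the splint in place and has no item for the skin before application. Routine nursing observations serve as the skin assessment, but only within the study period.
- **Interventions:** that period begins at application and runs "until removal of the splint and the exit photos are taken".
- **PICOT:** "Assessment for the primary outcome will be for the duration that" the splint is on the baby. There is no control group.

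On the state of the skin at entry:

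- **Recruitment** (and again Enrolment): "It is likely that most babies will have previously had an PIVC for treatment or fluids".
- **Background and rationale:** "Generally skin injuries related to the use of a PIVC and splint are caused by removing plasters attached to the skin". The same section says that most catheters in New Zealand and Australia are held with a splint and Elastoplast, and that skin is often damaged even when the tape is removed with care.
- **Exclusion criteria:** a skin condition excludes a baby only if it prevents the splint from being attached.

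On the outcome: under Harms, an adverse event is skin damage (irritation, injury or pressure areas) that the unit's senior clinician attributes to the splint. The proportion of babies with such an event is one of the two primary outcomes.

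**The concern.** The primary safety outcome is a causal judgement: was this skin damage due to the splint? Without a control group, the natural evidence is a comparison of the same limb before and after. The protocol fixes the after and leaves the before unspecified, although its own background gives reason to expect tape damage in some babies at entry.

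The error can run either way. Old tape damage found at removal may be charged to the splint, or damage from the splint may be excused as old. The first inflates the event rate and the second lowers it. In a study of 30 babies in which few or no events are expected, either matters. An analysis plan written later could not repair this, because an image not taken before application cannot be recovered.

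A smaller matter concerns the end of the window. Read literally, PICOT stops primary outcome assessment when the splint comes off, while Interventions and Images carry on to the exit photos. Skin under the splint may first be fully visible at removal, so the protocol should say plainly that findings at that moment count.

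**Working it through.** **Is a baseline specified anywhere?** The possible sources, taken in turn:

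1. Photos (Images, Study Assessments): with the splint on and after removal. None before.
2. Routine nursing observations (Study Assessments): used for the study period, which Interventions starts at application.
3. Exclusion criteria: these imply that someone looks at the skin, but only to decide whether the splint can be attached. No record is asked for, and lesser damage does not exclude.
4. Participant timeline: baseline data are ticked at enrolment, but their content is not described and no skin check is named.

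None of these specifies a record of the limb before application.

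**The protocol's own figure.** Inputs from the Sample size section: n = 30; "We do not expect any adverse events"; and with none observed, "the 95% upper band on the rate of adverse events will be less than 10% (3/30 = 0.1").

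- Rule of three: 3/n = 3/30 = 0.100.
- Exact one-sided 95% upper limit for 0/30: 1 − 0.05^(1/30) = 0.0950.
- Exact two-sided 95% upper limit for 0/30: 1 − 0.025^(1/30) = 0.1157.

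The stated figure is reproduced by the rule of three and by the one-sided exact limit. Primary Analyses plans exact 95% intervals without giving sidedness. A two-sided limit is already above 10% with no events; that is a separate matter.

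**Effect of misclassified babies.** For x events in 30, the exact upper limit is the value of p at which P(X ≤ x | 30, p) equals 0.05 (one-sided) or 0.025 (two-sided). For x = 1 this means solving (1 − p)^30 + 30p(1 − p)^29 = 0.05 or 0.025.

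| Events counted | One-sided upper limit | Two-sided upper limit |
|---|---|---|
| 0/30 | 9.5% | 11.6% |
| 1/30 | 14.9% | 17.2% |
| 2/30 | 19.5% | 22.1% |
| 3/30 | 23.9% | 26.5% |

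Read downwards, the table shows old damage counted as new. Read upwards, it shows splint damage dismissed as old.

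**How likely is at least one false event?** The documents give no rate, so this is illustration only. Suppose each baby independently has probability q of carrying old damage on the splinted limb that is then attributed to the splint. The chance of at least one false event is 1 − (1 − q)^30:

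- q = 2%: 1 − 0.98^30 = 45%
- q = 5%: 1 − 0.95^30 = 79%
- q = 10%: 1 − 0.90^30 = 96%

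**The case against.** The strongest reply is that the clinicians are not blind to the baby's earlier skin. Nurses already check skin and limbs as routine, so notes from before enrolment probably exist. The senior clinician may consult them, the Safety Committee reviews reported injuries, the baseline data may include skin, and the listed contents of the data sheet need not be complete. The earlier catheter may also have been on another limb, and the protocol does not say how that particular catheter was secured. This stands to the extent that a reader should not infer that old and new damage cannot be told apart, or that no record of the skin exists. The supportable statement is narrower: the protocol specifies no baseline for the study, so a primary outcome would rest on memory or on notes not collected for it.

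A reader might also infer that the study misses damage appearing after removal, that the event count is therefore biased downward, and that follow-up should be extended, for instance by 24 hours. The documents do not support this. The exit photos are taken after removal, nothing in the protocol says that splint damage appears late, and no rate or time course is given. What remains is the mismatch between the PICOT window and the exit photos.

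Finally, the shift from 0/30 to 1/30 would follow from any miscount. It shows how sensitive the bound is to one baby and does not measure how often this problem occurs. Nor do the documents make zero events a formal go/no-go rule: they expect none, state the bound if none is seen, and leave progression to a randomised trial as a possibility.

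**Conclusion.** The point holds in this form: attribution of skin damage to the splint, on which the primary safety outcome depends, has no specified before-state, while the protocol's own background makes earlier damage plausible in some babies. How many would have it on the splinted limb is unknown, and so are the size and net direction of any bias.

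What can be sized is the sensitivity of the result. One misclassified baby moves the one-sided upper limit from 9.5% to 14.9%, which crosses the 10% used to justify going on to a randomised trial. The two-sided limit moves from 11.6% to 17.2%. These figures assume 30 evaluable babies, exact binomial limits, and no other event. The chances of 45% to 96% of at least one false event depend wholly on assumed rates of 2% to 10%.

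This is worth correcting before recruitment, because the missing information cannot be collected afterwards.

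**What to change.** 1. **Images and data collection sheet:** add one standardised photo of the bare limb, with the same tape measure, and a one-line skin observation, both before the splint is applied. The order of cannulation and splinting is not stated. Since consent comes before the catheter is placed, the record could be made once the limb is chosen and before cannulation.
2. **Harms and Primary Outcome:** count as an adverse event only a skin change that is new or worse relative to that record and that the senior clinician attributes to the splint.
3. **PICOT:** align the window with Interventions and Images, so that skin findings at removal and on the exit photo count towards the primary safety outcome.

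The cost is one extra photo and one CRF line per baby, 30 of each. The Budget justification section already provides a camera for the data collection period. It is a small addition to bedside work that the protocol wants to keep low, and it changes neither the sample size nor the analysis. Any skin check after the exit photo is an option for the sponsor and is not required by this point.

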### **Outcomes**

# Primary Outcome

The proportion of babies in which the Pēpi Splint was determined by the bedside nurse to have supported the secured the PIVC for the required time. The proportion of babies who experience an adverse event related to the Pēpi Splint.

### Secondary outcomes

The acceptability of the Pēpi Splint as reported in the parents' response in the questionnaire The parents experience of participating in the Pēpi Splint project as reported in the questionnaire

### Participant timeline

	Enrolment	
TIMEPOINT	-t 1	Data collection
ENROLMENT:		
Eligibility screen	X	
Informed consent	X	
Recruitment		
Baseline data	Х	
Demographics and contacts	Х	
INTERVENTIONS:		
Pēpi Splint applied		X
Pēpi Splint removed		X
ASSESSMENTS:		
Data collection completed		X
Photos taken		X
Parent questionnaire		X

### Sample size

The primary reason for this Proof of Concept phase is to determine if the Pēpi Splint will support the PIVC and any adverse events related to the use of Pēpi Splint.

We do not expect any adverse events. We have determined that using a sample size of 30 where no adverse events have been observed, we can be assured that the 95% upper band on the rate of adverse events will be less than 10% (3/30 = 0.1). This will provide enough evidence to justify the progression to a randomised controlled trial.

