### Primary Analyses

For the splint to be considered for use in clinical care we need to know if it will hold the intravenous catheter in place and whether skin damage or irritation occurs.

Two exact 95% confidence intervals will be calculated, one for the proportion of babies in which the Pēpi Splint was judged by the clinical team to have supported the PIVC, and one for the proportion of babies who experience an adverse event. Secondary outcomes will be to determine the acceptability of the Pēpi Splint to both parents and clinical staff.

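### The adverse-event bound is the only quantified progression criterion and is called sufficient, while PIVC support, also a primary outcome, has no threshold

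*Protocol*

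**What the plan says.** The Sample size section names two reasons for the study: whether the splint supports the PIVC, and adverse events. It then deals only with the second. It states "We do not expect any adverse events", works from "using a sample size of 30 where no adverse events have been observed", derives a 95% upper bound below 10% from 3/30, and concludes: "This will provide enough evidence to justify the progression to a randomised controlled trial".

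Other sections set a wider condition. Background and rationale ends: "Should the Pēpi Splint be found to be effective and acceptable we may proceed to either an equivalence or superiority randomised controlled trial". The Project Summary and Significance sections say much the same, and Significance names both staff and parents as judges of acceptability. The specific aims under Research outcome include support of the catheter in what the splint has to show.

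Under Primary Outcome, the first measure is the proportion of babies in whom the bedside nurse judged the splint "to have supported the secured the PIVC for the required time". The second is the proportion with a splint-related adverse event. Under Primary Analyses, "Two exact 95% confidence intervals will be calculated", one for each proportion. Neither section gives a minimum, target or success count for support.

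**The concern.** The study exists to decide whether a randomised trial should follow. The protocol answers in two ways that do not agree: one section treats the safety result as sufficient, and three others also require effectiveness and acceptability. Only the safety side carries a number.

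The support proportion will be estimated with an interval, but nothing written in advance classifies that interval as success or failure. The judgement would fall to the Steering Committee, which according to the Project Summary analyses the data and according to Access to Data oversees interpretation and reporting. A bar set after the results are known can be fitted to them. The risk is that a harmless splint that secures the PIVC poorly goes forward, with the Sample size sentence cited as the justification.

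**Working it through.** **Inputs.** n = 30, single arm (PICOT, Sample size); 0 adverse events assumed and a 95% upper bound below 10% (Sample size); exact 95% confidence intervals (Primary Analyses). The documents give no bar and no expected value for support, so the bars and true rates used in step 3 are assumptions.

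**1. The plan's own figure.**
- Rule of three: 3/30 = 10.0%.
- Exact one-sided 95% upper bound at 0/30: 1 − 0.05^(1/30) = 9.50%, which is below 10%.
- Exact two-sided 95% upper limit at 0/30: 1 − 0.025^(1/30) = 11.57%, which is not below 10%.

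The stated figure reproduces, but only as a one-sided bound. With 1/30 the exact one-sided bound is 14.9%, so in practice the criterion means zero events.

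**2. What that criterion says about support.** It does not involve the support count. With 0/30 adverse events, the Sample size sentence is equally satisfied by any of these results (Clopper-Pearson 95% intervals):

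| Supported | Proportion | Exact 95% CI |
|---|---|---|
| 27/30 | 90% | 73.5 to 97.9% |
| 24/30 | 80% | 61.4 to 92.3% |
| 18/30 | 60% | 40.6 to 77.3% |

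No number in the protocol separates these rows into success and failure.

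**3. What a support bar could do at n = 30.** The table gives the exact two-sided 95% lower limit at each success count r, and the chance of reaching at least r if true support is 95%: P(X ≥ r) with X ~ Binomial(30, 0.95).

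| Count needed | Lower limit | Chance of reaching it, true support 95% |
|---|---|---|
| 27/30 | 73.5% | 93.9% |
| 28/30 | 77.9% | 81.2% |
| 29/30 | 82.8% | 55.4% |
| 30/30 | 88.4% | 21.5% |

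For 29/30 the sum is 30 × 0.95^29 × 0.05 + 0.95^30 = 0.339 + 0.215 = 0.554. For 30/30 the lower limit is 0.025^(1/30) = 88.4%, so a two-sided lower limit of 90% cannot be reached with 30 babies. In the other direction, a count of 27/30 would be reached 12.3% of the time if true support were 80% and 0.9% of the time if it were 70%.

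**The case against.** The strongest reply is that the Sample size sentence should not be read alone. It closes a sample-size justification that itself names PIVC support as a reason for the study. The Project Summary, Background and rationale, and Significance sections all require effectiveness and acceptability, and Background says only that the team *may* proceed. This stands. A reader might infer that the adverse-event bound is the only written progression rule, or that a splint with 18/30 support would have to go forward. The documents do not support either reading: a poor splint could be stopped under those other sections. What remains is that they give no figure, so stopping it would rest on judgement after the fact.

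A reader might also treat the lack of a comparator as the error. It is not. A single-arm proof-of-concept study is a declared choice (Trial design, PICOT), and comparison is left to the later trial. The statement that "data regarding the duration of PIVCs or the number required for any given baby are few" concerns duration and number of catheters, not the proportion supported.

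Nor is each baby's previous standard-splint PIVC a sound reference. Recruitment and Enrolment say only that an earlier PIVC is likely for most babies. The last catheter before a new one is needed is selected for having failed. Its hours in place and reason for removal would also measure something different from a nurse's judgement of support.

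Finally, a support bar could sit in a statistical analysis plan that is not shown. That would supply the missing figure, but the Sample size sentence would still call the safety result sufficient.

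**Conclusion.** The point holds in a limited form. The protocol contradicts itself on what justifies the randomised trial. The adverse-event bound is its only quantified criterion, and a primary outcome has no pre-set value that could settle the decision. Taken literally, the Sample size sentence is met at 0/30 adverse events with support as low as 18/30 (40.6 to 77.3%); read with the other sections, that result is simply left undecided. The contradiction rests on wording alone and needs no assumption. The support intervals assume n = 30 with all babies assessed. The chances of passing assume a true support rate that the documents do not give. The bound below 10% is correct only if meant as one-sided.

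**What to change.** Reword the end of the Sample size section so that progression needs all three of the following, and bring the Project Summary, Background and rationale, and Significance into line with it:

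- **Adverse events:** the bound below 10%, stated as an exact one-sided 95% bound (9.5% at 0/30). Note that the two-sided exact upper limit is 11.6%, so that the interval reported under Primary Analyses does not appear to contradict it.
- **PIVC support:** a minimum success count out of 30, fixed and recorded by the Steering Committee before the first baby is enrolled. The choice is the committee's; the counts from 27/30 to 30/30 in the working are illustrations of what each would exclude and how often it would be reached.
- **Acceptability:** as already required in Background and rationale and in Significance.

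The cost is a few sentences, one decision by the committee, and submission as an amendment if the protocol is already final. No extra babies, data items or tests are needed. The downside is that a good splint may miss a strict bar: at 29/30, one with true support of 95% would miss it about 45% of the time (1 − 0.554). The committee should see that trade-off before it chooses.
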